Study Protocol:

Open-label study of Maraviroc in Hospitalized Individuals Diagnosed with SARS-CoV-2

NCT04435522

Version Date: 11/6/2020

[name] MD, MS

Clinical Research Protocol

OPEN-LABEL STUDY OF MARAVIROC IN HOSPITALIZED INDIVIDUALS DIAGNOSED WITH SARS-COV-2

Version Date:	11/6//2020
Commercial Product:	Maraviroc
IND Number:	PIND 150411, IND exempt
Development Phase:	Phase 1
Sponsor:	Department of Medicine
Principal Investigator:	Name: [name] MD, MS
	[contact]
	[contact]
	E-mail: [contact]
Medical Monitor:	Name: [name] MD
	[contact]
	E-mail: [contact]

Version #: 2.8 Version Date: 11/6/2020 Page 1 of 30

TITLE	Open-Label Study of Maraviroc in Hospitalized Individuals Diagnosed with SARS-CoV-2
PRINCIPAL INVESTIGATOR	[name] MD, MS
SPONSOR	Department of Internal Medicine
SITE	Rhode Island Hospital The Miriam Hospital
RATIONALE	CCR5 antagonism in SARS-CoV-2 may alter cell trafficking of inflammatory cells, reduce activation of platelets, and may have a role in reversing lymphopenia. Maraviroc may also have anti-viral properties related to binding to SARS-CoV-2 Main Protease beyond its mechanism as a CCR5 antagonist.
STUDY DESIGN	Single-arm, Open-Label, Proof-of-Concept
PRIMARY OBJECTIVE	To establish whether Maraviroc, used at its approved dosage for HIV, is safe and effective in hospitalized patients with SARS-CoV-2.
SECONDARY OBJECTIVES	Investigate the relationship between reduction of inflammatory and other biomarkers (such as IL-6, CCL5, etc.) later in the course of infection and avoidance of respiratory decompensation and death.
NUMBER OF SUBJECTS	16 subjects
SUBJECT SELECTION CRITERIA	 Inclusion Criteria: Male or female ≥ 18 years of age at time of screening Documentation of a SARS-CoV-2 diagnosis as evidenced by positive SARS-CoV-2 PCR within twelve days at time of screening Chest radiography consistent with multi-focal pneumonia or air-space disease Written informed consent obtained from subject and ability for subject to comply with the requirements of the study. Subject able to safely swallow pills or receive Maraviroc through a nasogastric or orogastric tube. Exclusion Criteria: Subjects who are pregnant, breastfeeding, or unwilling to practice birth control during participation in the study. Subjects with the presence of a condition or abnormality that in the opinion of the Investigators would compromise the safety of

Version #: 2.8 Version Date: 11/6/2020 Page 2 of 30

	 the patient or the quality of the data. This includes, but is not limited to, recent myocardial infarction in past 6 months, neurological, psychiatric, endocrine, or neoplastic diseases that are judged to interfere with participation in the study. Subjects with known diagnosis of human immunodeficiency virus infection (HIV) Subjects enrolled in another interventional trial (including one for COVID-19) that excludes participation in other trials or includes a potent CYP3A inhibitor or inducer (e.g. lopinavir-ritonavir). Subjects with ESRD or severe renal failure who are taking potent (moderate or strong) CYP3A inhibitors or inducers
TEST PRODUCT, DOSE, AND ROUTE OF ADMINISTRATION	Maraviroc will be administered orally twice daily for seven days.
DURATION OF SUBJECT PARTICIPATION AND DURATION OF STUDY	Subjects will be on study for up to 35 days Treatment: 7 days Follow-up: 28 days The total duration of the study is expected to be 4 months. 2 months for subject recruitment, 1 for final subject follow-up and 1 month for data run-off and analysis.
CONCOMMITANT MEDICATIONS	Prohibited: Lopinavir-Tenofovir Hydroxychloroquine Ivermectin
EFFICACY EVALUATIONS	
PRIMARY ENDPOINT	• In this proof-of-concept trial, the study team is chiefly concerned with safety and tolerability of Maraviroc in subjects diagnosed with SARS-CoV-2. The primary endpoint is rate of subjects who complete the 7-day course of Maraviroc without discontinuation for serious adverse event or death. Additional endpoints include the percent of study population reaching clinical improvement, defined as time from enrollment to an improvement of two points on a seven-category ordinal scale (defined below), at Day 7.
SECONDARY ENDPOINTS	Time to improvement to Score of 2 or less (Days) based on Ordinal scale: 1, not hospitalized with resumption of normal activities; 2, not hospitalized, but unable to resume normal

Version #: 2.8 Version Date: 11/6/2020 Page 3 of 30

	 activities OR hospitalized pending disposition, not requiring COVID-related care; 3, hospitalized, not requiring supplemental oxygen; 4, hospitalized, requiring supplemental oxygen; 5, hospitalized, requiring nasal high-flow oxygen therapy, noninvasive mechanical ventilation, or both; 6, hospitalized, requiring ECMO, invasive mechanical ventilation, or both; and, 7, death. Change in biomarker levels (CCL5, IL-6, Chi311, etc) from time of enrollment to completion of therapy or live discharge from the hospital (whichever comes first) 7-, 14- and 28-day all-cause-mortality 	
	Days on mechanical ventilation	
SAFETY EVALUATIONS	Daily, multi-disciplinary safety monitoring with interim analysis after 8 subjects have received four or more doses of Maraviroc.	
PLANNED INTERIM ANALYSES	Exposure-adjusted rates of adverse events and those resulting in discontinuation will be calculated at the point in which 8 patients have received more than four doses of treatment. Serious adverse events will be monitored by the study team on an ongoing basis throughout the study.	
STATISTICS Analysis Plan	 Rates of adverse events by severity and rate of completion of therapy. Change in biomarkers compared to clinical improvement Percent of study population reaching clinical improvement at Day 7 will be compared to published results from Remdesivir for 5 or 10 Days in Patients with Severe COVID-19, and other available clinical trials including The Randomized Evaluation of COVID-19 therapy (RECOVERY) Trial. 	

Version #: 2.8 Version Date: 11/6/2020 Page 4 of 30

TABLE OF CONTENTS

1	BACKGROUND7		7
2	STUDY RATIONALE9		
3 STUDY OBJECTIVES			10
	3.1	Primary Objective	10
	3.2	Secondary Objectives	10
4	STUI	DY DESIGN	10
	4.1	Study Overview	10
5	CRIT	TERIA FOR EVALUATION	10
	5.1	Primary Efficacy Endpoint	10
	5.2	Secondary Efficacy Endpoints	10
6	SUB	JECT SELECTION	11
	6.1	Study Population	11
	6.2	Inclusion Criteria.	11
	6.3	Exclusion Criteria	11
7	CON	CURRENT MEDICATIONS	11
	7.1	Allowed	11
	7.2	Prohibited	12
8	STUI	DY TREATMENTS	12
	8.1	Method of Assigning Subjects to Treatment Groups	12
	8.2	Formulation of Test Product	12
	8.3	Supply of Study Medication at the Site	12
	8.4	Study Medication Accountability	13
	8.5	Measures of Treatment Compliance	14
9	STUI	DY PROCEDURES AND GUIDELINES	14
	9.1	Clinical Assessments	14
	9.2	Clinical Laboratory Measurements	15
	9.3	Research Laboratory Measurements	15
10	EVA	LUATIONS BY VISIT	16
	10.1	Screening/Enrollement (Day 0).	16
	10.2	Visit 1 (Day 1)	16

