3.2 Secondary Objectives

The secondary objective is to investigate the relationship between reduction of inflammatory markers (such as IL-6, CCL5, etc.) and clinical outcomes, including avoidance of respiratory decompensation and death.

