5 CRITERIA FOR EVALUATION

5.1 Primary Endpoint

This proof-of-concept trial will evaluate safety and tolerability of Maraviroc in SARS-CoV-2 infected patients. The primary endpoint is rate of patients who complete the 7-day course of Maraviroc without discontinuation for adverse events, hospitalization, or death. Additional endpoints include the percent of study population reaching clinical improvement, defined as time from enrollment to an improvement of two points on a seven-category ordinal scale (defined below), at Day 7.

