5.2 Secondary Endpoints

- Time to clinical improvement, defined as time from enrollment to an improvement of two points on a seven-category ordinal scale (defined below) or live discharge from the hospital, whichever comes first
 - Ordinal scale: 1, not hospitalized with resumption of normal activities; 2, not hospitalized, but unable to resume normal activities OR hospitalized pending disposition, not requiring COVID-related care; 3, hospitalized, not requiring supplemental oxygen; 4, hospitalized, requiring supplemental oxygen; 5, hospitalized, requiring nasal high-flow oxygen therapy, noninvasive ventilation, or both; 6, hospitalized, requiring ECMO, invasive mechanical ventilation, or both; and, 7, death.
- Change in cytokine levels from time of enrollment to completion of therapy or live discharge from the hospital (whichever comes first)
- 7-, 14- and 28-day all-cause-mortality
- Time to improvement to Score of 2 or less (days)
- Days on mechanical ventilation

Version #: 2.8 Version Date: 11/6/2020 Page 10 of 30

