15 STATISTICAL METHODS AND CONSIDERATIONS

Prior to the analysis of the final study data, a detailed Statistical Analysis Plan (SAP) will be written describing all analyses that will be performed. The SAP will contain any modifications to the analysis plan described below.

Version #: 2.8 Version Date: 11/6/2020 Page 27 of 30

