15.3 Analysis of Endpoints

Continuous data obtained will be expressed by mean ± standard deviation (SD) or interquartile range, as applicable. Categorical variables will be reported as frequency and percentages. ICU LOS (and mechanical ventilation LOS, respectively) will be regressed on available laboratory and biomarker data using multivariable linear regression. All analysis will be conducted in a professional statistical program. Mortality and percent of study population reaching clinical improvement at Day 7 will be compared to published results from Remdesivir for 5 or 10 Days in Patients with Severe COVID-19, and other available clinical trials including The Randomized Evaluation of COVID-19 therapy (RECOVERY) Trial.

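### The synopsis relates biomarker change to clinical improvement rather than to respiratory decompensation or death, which its secondary objective names, and no planned analysis relates biomarkers to death

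*Combined protocol and SAP*

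**What the plan says.** **Objective.** The synopsis relates the reduction of inflammatory and other biomarkers "later in the course of infection and avoidance of respiratory decompensation and death". Section 3.2 is wider and speaks of "clinical outcomes, including avoidance of respiratory decompensation and death".

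**Synopsis analysis.** The statistics row has one line on this question: "Change in biomarkers compared to clinical improvement". It names no day, test or significance level.

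**Clinical improvement.** Section 5.1 has it as a Day 7 endpoint, "defined as time from enrollment to an improvement of two points on a seven-category ordinal scale (defined below), at Day 7". Section 5.2 has a time-to-event version that also counts discharge: "or live discharge from the hospital, whichever comes first".

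**Body analysis.** Section 15.3 states that "ICU LOS (and mechanical ventilation LOS, respectively) will be regressed on available laboratory and biomarker data using multivariable linear regression". Death appears there only in an external comparison: "Mortality and percent of study population reaching clinical improvement at Day 7 will be compared to published results".

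**Data.** Section 5.2 lists all-cause mortality and ventilator days as endpoints. Section 16.1 has the seven-category score captured daily. The objectives, endpoints and analysis sections do not define respiratory decompensation.

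**The concern.** Avoiding decompensation and improving by two points are different outcomes, and neither is the complement of the other. A subject who stays at score 4 has avoided decompensation but has not improved. A subject who goes from 4 to 6, or dies, has not improved either. The synopsis comparison puts both in one group. In the time-to-event version, a subject who is intubated and later recovers can even count as improved.

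If a falling biomarker marks the subjects who escape respiratory failure, the contrast of interest lies largely inside the group that did not improve, where this comparison cannot see it. The trial could then report no relation, or a relation with speed of recovery, as its answer to a question about respiratory failure and death.

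**Working it through.** The documents give no sample-size, power or alpha figure for the biomarker question, so there is no stated figure to reproduce. The check compares the texts and then illustrates the size of the effect.

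**1. Which planned analysis reaches which outcome**

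| Outcome named in the objective | Synopsis comparison (improvement) | Section 15.3 length-of-stay regression | Section 15.3 external comparison |
|---|---|---|---|
| Respiratory decompensation | Pooled with stable subjects | Indirect: duration, not occurrence | Not addressed |
| Death | Pooled with stable subjects | Not modelled; early death shortens the stay | Compared with published trials, not with biomarkers |

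The regression does not say how subjects with no ICU or ventilator time are handled. It would also miss an escalation to high-flow oxygen or noninvasive ventilation outside the ICU.

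**2. Inputs for the illustration**

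- n = 16 (Section 4.1).
- From the lopinavir-ritonavir trial described in Section 1: 45.5% improved and 15.2% dead at Day 14; 16% eventually ventilated.
- Assumptions not in the documents: these rates carry over to this trial; 4 subjects decompensate or die; the biomarker change is shifted by 1.5 SD in those 4 only; normal data; two-sided exact rank test at 0.05.

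**3. Make-up of the groups at the Day 14 rate**

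- Improved: 16 × 0.455 = 7.3. Not improved: 16 × 0.545 = 8.7. This is about 7 v 9.
- Deaths: 16 × 0.152 = 2.4, which is 0.152/0.545 = 28% of those not improved. The other 72% are survivors of mixed status.
- Ventilated: 16 × 0.16 = 2.6.

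**4. Dilution**

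With 4 decompensators among 9 non-improvers, the mean shift in that group is 1.5 × 4/9 = 0.67 SD. In SD units, the standard error of a mean difference is √(1/a + 1/b), ignoring the extra spread within the mixed group.

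- Improved v not improved, 7 v 9: √(1/7 + 1/9) = 0.50, and 0.67/0.50 = 1.3 standard errors.
- Decompensated or dead v the rest, 4 v 12: √(1/4 + 1/12) = 0.58, and 1.5/0.58 = 2.6 standard errors.

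The 7 v 9 split has the smaller standard error. Its disadvantage comes entirely from pooling, which more than halves the difference to be found.

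**5. Simulated power under the same assumptions**

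- Direct comparison, 4 v 12: about 60% (about 50% for 3 v 13 and 65% for 5 v 11, with the shift in the 3 or the 5).
- Improved v not improved, 7 v 9: about 13%.

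**6. Limit of the direct comparison**

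At a 16% event rate, P(at most one event in 16) = 0.84^16 + 16 × 0.16 × 0.84^15 = 0.061 + 0.187 = 0.25.

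**The case against.** The strongest reply is that the plan should not be judged on one synopsis line. A reader might infer that the stated question goes untested, or that decompensation is never recorded. The documents support neither inference:

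- Section 15.3 regresses ICU and ventilation length of stay on biomarkers, which bears on decompensation.
- Section 3.2 words the objective broadly enough to take in improvement as a clinical outcome. Only the synopsis wording is narrow.
- Ventilator days and mortality are endpoints in 5.2. Intubation is recorded at the daily visits and in later follow-up, and the ordinal score is captured daily.

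A reader might also take improvement at Day 7 as the comparator. At the cited 6% rate that gives 16 × 0.06 = 0.96 improvers, so about 1 v 15, a split that looks hopeless beside any other. But the synopsis line names no day. At the Day 14 rate the split is about 7 v 9, which is better balanced than 3 v 13, 4 v 12 or 5 v 11, so a general claim of better precision for the event-based split fails.

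It is also fair to say that the 1.5 SD shift is assumed, that no rank test or alpha is planned, and that Section 15 promises a later document: "The SAP will contain any modifications to the analysis plan described below".

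These points narrow the concern but do not remove it. Length of stay measures duration rather than occurrence and can reward early death. Nothing now written relates biomarkers to death. The promised analysis plan may close the gap, but nothing in the protocol requires it to.

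**Conclusion.** The mismatch stands. The synopsis analysis uses an outcome other than the one its secondary objective names, and its comparison group mixes stable, decompensated and dead subjects. Section 15.3 covers decompensation only indirectly, and death is not related to biomarkers in any planned analysis. This conclusion rests on the text alone.

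The power figures (about 60% against about 13%) are illustrative. They depend on the assumed 1.5 SD shift in 4 decompensators, on rates borrowed from another trial, and on a test that the plan does not specify. With 16 subjects in one arm, any result is exploratory. The point is a cheap improvement in how well the analysis fits its question. It does not show that the trial cannot address that question.

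**What to change.** 1. Add to Section 5.2 an outcome of respiratory decompensation or death by Day 28, derived from the daily ordinal score. Two forms would serve: worsening from baseline to a higher category, with the threshold chosen by the sponsor and stated in advance; or the worst post-baseline score, with death as 7.
2. Make it the outcome of the biomarker comparison in the synopsis and Section 15.3. Use an exact rank test for the binary form or a rank correlation for the worst score.
3. Use biomarker change measured before the event. State how subjects are handled whose event or death comes before the second sample, which Section 4.1 schedules for Day 3.
4. Keep the improvement and length-of-stay analyses as secondary. State how deaths and subjects with no ICU or ventilator time enter the regression.
5. Align the wording of the objective between the synopsis and Section 3.2.

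The cost is one derived variable from scores already collected and one more exploratory analysis in 16 subjects. The binary form may yield too few events to be informative; the worst-score form depends less on the event count.

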1 BACKGROUND

Severe Acute Respiratory Syndrome Coronavirus 2 (SARS-CoV-2) is the cause of Coronavirus disease 2019 (COVID-19) and was first reported in Wuhan, China in December 2019¹. Though a wide spectrum of clinical manifestations exists, patients often present with mild upper respiratory symptoms, progressing in some cases to a multifocal pneumonia with multiorgan compromise². As the natural history of SARS-CoV-2 is further understood, increased attention has been devoted to understanding disease progression and notably severe respiratory complications which are described as occurring after 7-14 days after the onset of illness. Initial retrospective studies of confirmed COVID-19 cases in tertiary hospitals in Hubei Province, China, revealed a range of 1-20 days for the progression of respiratory distress following illness onset^{1,2,3}. The clinical course of COVID-19 infections appears to have a high degree of heterogeneity, with some remaining relatively uncomplicated, some progressing to a moderate pneumonia, and others developing severe, progressive pneumonia characterized by dyspnea, tachypnea, and hypoxia. Increased levels of IL-6 and decreased levels of lymphocytes have been reported in severe illnesses in a retrospective cohort of patients from Jinyintan and Wuhan hospitals. Older age and common comorbidities including hypertension, diabetes, and coronary artery disease have been associated with increased mortality³.

In the negative randomized, controlled, open-label trial of Lopinavir-Ritonavir involving patients with COVID-19 and oxygen saturation of less than 94% on room air, 70% of patients required supplemental oxygen and 15% required high-flow nasal cannula or non-invasive mechanical ventilation on presentation. Only one patient required intubation on presentation, but 16% would eventually require mechanical ventilation during their hospitalization. At Day 7, only 6% of the subjects in the Lopinavir-Ritonavir reached clinical improvement of 2 points on a 7-point ordinal scale. At day 14, 45.5% of subjects reached 2-point clinical improvement, 15.2% of subjects had died, and 28% continued to require non-invasive and nasal cannula support. This early study highlighted the lengthy duration of hospitalization and late progression of respiratory failure in COVID-19.

SARS-CoV-2 is an RNA coronavirus that enters the cell through an endosomal route, during which the virus attaches to Angiotensin-Converting-Enzyme-2 receptor, subsequently endocytosed into a vesicle and released into the cytoplasm of the cell via cathepsin-cleaved spike protein. The virus can also attach to Transmembrane Serine Protease 2 (TMPRSS2) to directly enter the cell via fusion with the cell membrane. Once in the cell the viral mRNA is transcribed via RNA-dependent RNA polymerase to create more

Version #: 2.8 Version Date: 11/6/2020 Page 7 of 30

¹ Li Q, Guan X, Wu P, et al. Early Transmission Dynamics in Wuhan, China, of Novel Coronavirus–Infected Pneumonia. *N Engl J Med*. 2020;382(13):1199-1207. doi:10.1056/NEJMoa2001316

² Huang C, Wang Y, Li X, et al. Clinical features of patients infected with 2019 novel coronavirus in Wuhan, China. *Lancet*. 2020;395(10223):497-506. doi:10.1016/S0140-6736(20)30183-5

³ Zhou F, Yu T, Du R, et al. Clinical course and risk factors for mortality of adult inpatients with COVID-19 in Wuhan, China: a retrospective cohort study. *Lancet*. 2020;395(10229):1054-1062. doi:10.1016/S0140-6736(20)30566-3

⁴ Cao B, Wang Y, Wen D, et al. A trial of lopinavir-ritonavir in adults hospitalized with severe COVID-19 N Engl J Med. 2020. doi:10.1056/NEJMoa2001282

genome RNA. Additionally, sub-genomic mRNAs are translated to create proteins including proteases and replicates, such as papain-like protease, 3C-like protease (also known as main protease) and RNA-dependent DNA polymerase (RdRp). ⁵These proteins serve as potential targets for anti-virals. Remdesivir, an anti-viral that received FDA Emergency Use Authorization for use in COVID-19, targets RdRp. Other FDA approved medications have been identified as potential drugs to re-purposing. Virtual screening of 2388 FDA approved medications for binding affinity to the SARS-CoV-2 3C-like protease (main protease), which is essential for processing the polyproteins required for viral assembly, revealed the CCR5-antognist Maraviroc to have the second-highest binding affinity. Further molecular conformational dynamic simulations and the MMPBSA approach are ongoing to provide further estimation of the binding affinity of Maraviroc to binding site on the 3C-like protease.⁶

A growing body of literature is addressing the complex pathophysiology underlying COVID-19 infections to better understand human responses to the novel coronavirus. Given the similarities between other coronaviruses, including SARS-CoV-1, and SARS-CoV-2, pathogenesis of SARS-CoV-2 has been extrapolated from SARS-CoV-1 disease in animal models. In senescent mouse models of SARS-CoV-1 infection, increased expression of chemokine mRNA was observed in the lungs early and late in the infection, in a "biphasic" manner. Compared to controls, a >9-fold increase in CCL5/RANTES and 4-fold increase in CCR2 mRNA were detected around days 7-9 of infection, when histopathologic evidence of pneumonitis was noted. Additionally, inflammatory cells recruited to the lungs early and late in the infection corresponded to the biphasic expression of aforementioned chemokines.⁷

CCR5 antagonism may play a role in diminishing acute lung injury correlating to chemotaxis of neutrophils and other effector cells late in the course of Coronavirus infection. Mouse models of acute lung injury have demonstrated that treatment with a CCR5 antagonist, Maraviroc, significantly reduced lung neutrophil infiltration, inhibited lung edema formation, and prevented histological tissue alterations. In addition, in-vitro studies of Maraviroc have demonstrated its ability to effectively inhibit macrophage and dendritic cell chemotaxis.

Version #: 2.8 Version Date: 11/6/2020 Page 8 of 30

⁵ Simmons G, Zmora P, Gierer S, Heurich A, Pöhlmann S. Proteolytic activation of the SARS-coronavirus spike protein: cutting enzymes at the cutting edge of antiviral research. Antiviral Res. 2013;100(3):605-614. doi:10.1016/j.antiviral.2013.09.028

⁶ A. Shamsi, T. Mohammad, S. Anwar, F. MohamedAl Ajmi, A. Hussain, M.T. Rehman, A. Islam, M.I. Hassan Glecaprevir and Maraviroc are high-affinity inhibitors of SARS-CoV-2 main protease: possible implication in COVID-19 therapy. *Bioscience Reports*, 40 (2020) 10.1042/BSR20201256

⁷ Chen J, Lau YF, Lamirande EW, et al. Cellular Immune Responses to Severe Acute Respiratory Syndrome Coronavirus (SARS-CoV) Infection in Senescent BALB/c Mice: CD4+ T Cells Are Important in Control of SARS-CoV Infection. *J Virol*. 2010;84(3):1289-1301. doi:10.1128/jvi.01281-09

⁸ Grommes J, Drechsler M, Soehnlein O. CCR5 and FPR1 mediate neutrophil recruitment in endotoxin-induced lung injury. *J Innate Immun*. 2014;6(1):111-116. doi:10.1159/000353229

⁹ Rossi R, Lichtner M, De Rosa A, et al. In vitro effect of anti-human immunodeficiency virus CCR5 antagonist maraviroc on chemotactic activity of monocytes, macrophages and dendritic cells. *Clin Exp Immunol*. 2011;166(2):184-190. doi:10.1111/j.1365-2249.2011.04409.

Chitinase 3-like 1 (Chi311, also called as YKL-40) is a powerful inhibitor of epithelial cell death and oxidant induced lung injury. Mice that lack Chi311 are particularly susceptible to the ravages induced by hyperoxia and other exposures that induce Acute Lung Injury (ALI). Studies have demonstrated that the expression levels of Chi311 in the lung were significantly decreased by the RIG-like helicase (RLH) immune activation, the well-defined host sensing mechanism of RNA viruses like SARS-CoV-2. These studies may suggest that the expression levels of Chi311 can be used as a sensitive biomarker of SARS-CoV-2 infection that predict disease severity and progression.

Recognizing that the relationship between the immune response and chemokine signaling are dynamic and complex, studies are needed to explore CCR5 antagonism as a possible therapeutic target for SARS-CoV-2 infections. This study proposes that CCR5 antagonism prior to the second wave of inflammatory mediator expression may reverse lymphoid depletion and may alter cell trafficking of inflammatory cells, both increasing viral control capacity and dampening damage to lung tissue, respectively.

